#### **5.2.7 Laboratory Assessments**

CBC/differential, electrolytes, BUN, creatinine, glucose, albumin, AST, ALT, total bilirubin, alkaline phosphatase, PT, PTT, and Urinalysis.

#### **5.2.8 Imaging assessments Phase I**

Tumor response will be assessed according to RECIST Version 1.1 using standard contrast-enhanced computed tomographic scanning of the chest, abdomen and pelvis. In the case of iodine contrast allergy or reaction, either non-contrast-enhanced or MRI scanning can be performed. Patients should have at least one documented measurable lesion (per RECIST v1.1) or in the absence of measurable disease, have at least one lytic or mixed (blastic/lytic) bone lesion at study entry.

Imaging assessments will be performed at screening within 28 days prior to first dose of study treatment, at 8 weeks (+/- 1 week) from day one of study treatment and subsequently every 8-12 weeks (+/- 2 weeks) thereafter.

Tumor response should be assessed using the same imaging method throughout the study.

### **5.2.9 Imaging assessments Phase II**

Methods for ultrasound evaluation and volumetric measure of response

Grayscale and power Doppler ultrasound will be performed on the breast and regional nodal basins using a Philips iU22 system or Sonoline Antares systems equipped with a 5- to 13-MHz broadband linear transducer. Ultrasound images of the index tumors and index nodes will be captured in the longitudinal and transverse planes with three dimensions measured. The size of the index tumors and index nodes will be reported in three dimensions to allow for volumetric calculation. The percent change in volume will then be calculated and reported to determine response.

## **5.3 Correlative Biomarker Studies**

### **5.3.1 Biopsies, Tissue Handling and Analysis**

All biopsies on Phase I are optional and will be done with appropriate image guidance.

Biopsies for Phase II are mandatory and will be done under ultrasound guidance by a member of the research team using standard of care imaging-guided biopsy. Local anesthesia and hemostasis protocols will be used as per standard protocol. Core needles of 18 or 16G size will be used and 3-4 core biopsies will be obtained. The first core will be placed in standard 10% formalin, and all other cores will be placed in a cryovial and snap frozen in liquid nitrogen.

All of the correlative studies (unless otherwise indicated) will be performed in the laboratory of [name] located in the Zayed building at [name]. For all the correlative analysis we will use tumor tissues collected from the biopsies and at surgical resections.

Cyclin E, and Rb immunohistochemistry (IHC) assays. FFPE tumor tissue slides will be prepared from paraffin imbedded blocks per standard methodologies and subjected to IHC analysis with 2 different antibodies: cyclin E and Rb:

Cyclin E: the anti-human C-19 polyclonal antibody (Santa Cruz Biologicals) at 1:2000 dilution will be used to stain each slide. Each slide will be scored for percent nuclear and percent cytoplasmic positive staining. Only tumor cells with greater than 5% nuclear or cytoplasmic positivity are considered as cyclin E positive. Nuclear and cytoplasmic staining scores are assigned according to the staining intensity (0 = no staining, 1 = blush staining, 2 = weak staining, 3 = intermediate staining and 4= strong staining). The nuclear and cytoplasmic scores are then combined, and four immunophenotypes are identified. First, breast tumors will be considered to be negative for cyclin E when staining is not detected in the nuclei or cytoplasm (phenotype 1). Second, in cases determined to be cyclin E+, if the nuclear staining score exceeded the cytoplasmic score, cyclin E expression is defined as predominantly nuclear (phenotype 2). Third, when the nuclear and cytoplasmic staining scores are equal,

cyclin E expression is considered to be both nuclear and cytoplasmic (phenotype 3). Fourth, if the cytoplasmic staining score is higher than the nuclear score, cyclin E expression is considered to be predominantly cytoplasmic (phenotype 4).

Rb: The anti-human Clone 4H1 mouse monoclonal antibody (Cell Signaling Technology, Denvers, MA) at 1:100 dilution will be used to stain each slide. Each slide will be scored separately for intensity of staining and percentage of positive cells. Staining intensity will be scored as follows: 0, no staining; 1, weak positive (faint yellow staining); 2, intermediate positive; and 3, strong positive (brown staining). The number of positive cells will visually be evaluated and stratified as follows: <1%, 0 (negative); 1 to <5% positive cells, 1 (weak); 5-50% positive cells, 2 (moderate); >50% positive cells, 3 (strong). The sum of the staining intensity and percentage of positive cell scores will be used to determine the staining index for each section, with a minimum score of 0 and maximum score of 6; scores >1 will be defined as Rb positivity.

### **5.3.2 Whole Blood/Plasma Biospecimens**

Blood specimens (Phase II only) will be collected as shown on Table 2 at baseline, days 15 and 29 for patients on the “window” option and for those who stay on study until surgery will be collected on days 43, 57 and every 4 weeks thereafter until surgery. Each blood draw will be to collect three tubes – one for plasma (8 mL CPT top) and the other for serum (6 mL red top) and one for whole blood (6 mL lavender). Blood will be processed immediately following collections – tubes will be gently inverted and kept at room temperature prior to centrifuging, and clotted tube (red top) will have serum aspirated, while the green top tube will have plasma aspirated – both being aliquoted in 0.5 mL cryovials and placed in a -20°C freezer (and stored long term at -80°C). A laboratory protocol contains additional details.

### **5.3.3 Ki67 Tumor Assay and Scoring**

CLIA-approved Ki67 staining will be performed using anti-Ki67 rabbit monoclonal antibody (isotype IgG1κ, clone MIB-1, DAKO) in the diagnostic Immunohistochemistry Laboratory of Department of Pathology using an established protocol. Briefly this protocol includes de-paraffinization (30 minutes at 72°C) and rehydration with antigen retrieval performed at 100°C for 20 minutes with Tris-EDTA buffer, pH 6.0.

Endogenous peroxidase is blocked with 3% peroxide for 5 minutes. Primary anti-Ki-67 antibody (Dako, clone MIB-1) is applied at 1:100 dilution for 15 minutes. Post primary antibody detection is carried out using a commercial polymer system (Bond Polymer Refine Detection, Leica), and stain development is achieved by incubation with DAB and DAB Enhancer (Leica).

Ki67 staining will be evaluated in whole tissue sections without focusing on the hot spots. The staining will be quantitatively assessed by automated image analysis using the Aperio ScanScope AT2 scanner (Leica Biosystems, Inc., [name]). All Ki67 immunostained slides will be scanned at 20 X magnification. As Ki67 is a nuclear stain, the Genie nuclear v9.1 algorithm will be used to create a custom-made classifier. A color graphic phase of image analysis is afterward performed using red, orange, and yellow (high, medium, and low reaction, respectively) to represent positive cells, and blue to represent negative ones. A curvature threshold adjustment is made to de-cluster or

break up large groups of closely apposed nuclei when needed. The original factory algorithm is also adjusted to avoid false positives by lowering the Cytoplasmic Intensity settings. All algorithm adjustments are tested to assure accurate detection of positive and negative nuclei.

#### **5.4 Banked Biospecimens**

Leftover blood and tumor samples which are not consumed for planned study testing will be retained for potential additional testing at a later date (i.e. if newer technologies become available) under the same objectives. Samples will be retained at a secure storage facility (in the laboratory of [name] located in the Zayed building at [name]) in case there is need for retesting or additional testing. Samples will be stored for up to 10 years or until termination of this study. These may be used for future studies only as approved by the MD Anderson IRB and the Principal Investigator.

### **6.0 INVESTIGATIONAL AND NON – INVESTIGATIONAL AGENTS**

#### **6.1 Palbociclib**

##### **6.1.1 Description of palbociclib**

Palbociclib is an inhibitor of cyclin-dependent kinase (CDK) 4 and 6, which are downstream of signaling pathways that lead to cellular proliferation. In vitro, palbociclib reduces cellular proliferation of ER-positive breast cancer cell lines by blocking progression of the cell from G1 into S phase of the cell cycle. Treatment of breast cancer cell lines with the combination of palbociclib and endocrine therapies leads to decreased retinoblastoma protein (Rb) phosphorylation resulting in reduced E2F expression and signaling, and increased growth arrest compared to treatment with each drug alone. In vitro treatment of ER-positive breast cancer cell lines with the combination of palbociclib and antiestrogens leads to increased cell senescence, which was sustained for up to 6 days following drug removal. In vivo studies using a patient-derived ER-positive breast cancer xenograft model demonstrated that the combination of palbociclib and letrozole increased the inhibition of Rb phosphorylation, downstream signaling and tumor growth compared to each drug alone (Pfizer Pharma United States product insert (USPI), (2015). Highlights of Prescribing Information; IBRANCE® (palbociclib) for oral use. New York: Pfizer, Inc. – details are contained in the package insert in Appendix A).

Complete information for palbociclib may be found in the single reference safety document (SRSD), which for this study is the Pfizer Investigator Brochure for Palbociclib (PD-0332991).

##### **6.1.2 Source of palbociclib**

Palbociclib will be provided by Pfizer Inc. Palbociclib commercial supply will be supplied as 75 mg capsules in High Density Polyethylene (HDPE) bottles, labeled according to investigational pharmacy procedures.

##### **6.1.3 Preparation and dispensing**

Qualified site personnel will provide adequate palbociclib supplies for patient to take home until next scheduled visit.

Patients will receive a drug diary to document dosing. The completed diary must be returned

to the site at the next study visit.

#### **6.1.4 Dosing of palbociclib and dose adjustments for palbociclib (holding, discontinuation)**

Patients should be instructed to swallow palbociclib capsules whole and not to manipulate or chew them prior to swallowing. No capsule should be ingested if it is broken, cracked, or otherwise not intact. Patients should be encouraged to take their dose at approximately the same time each day. Patients should be instructed to record daily administration in the patient diary.

Patients should take palbociclib with food.

- Patients who miss a day's dose entirely must be instructed NOT to "make it up" the next day.
- Patients who vomit any time after taking a dose must be instructed NOT to "make it up," and to resume treatment the next day as prescribed.
- Patients who inadvertently take 1 extra dose during a day must be instructed to skip the next day's dose.

Dose adjustments and patient discontinuation criteria are as follows:

- Palbociclib will be held for grade 3 or 4 neutropenia, and CBC/diff will be checked in one week intervals, with treatment resumed at the same dose when neutropenia has recovered to Grade  $\leq 2$ . If more than two weeks are required for recovery to Grade  $\leq 2$ , the dose will be lowered to 75 mg by mouth twice a week.
- Once palbociclib dose has been lowered, it will not be re-escalated. If criteria for another dose reduction are met, the patient must be permanently discontinued
- Any episode of febrile neutropenia (fever  $\geq 38.5^{\circ}\text{C}$ ) with ANC  $< 1000$  will require discontinuation
- For Grade  $\geq 3$  non-hematologic toxicity attributed to palbociclib, palbociclib will be held until the toxicity in question resolves to Grade  $\leq 1$  or Grade  $\leq 2$  if not considered a risk to the patient.
- Any patient with liver function test abnormalities meeting Hy's Law criteria must be permanently discontinued

## **6.2 Hydroxychloroquine**

### **6.2.1 Description of hydroxychloroquine (HCQ):**

Hydroxychloroquine (HCQ) is a small molecule drug that is indicated for the suppressive treatment and treatment of acute attacks of malaria due to *Plasmodium vivax*, *P. malariae*, *P. ovale*, and susceptible strains of *P. falciparum*. It is also indicated for the treatment of discoid and systemic lupus erythematosus, and rheumatoid arthritis, and often used for overlap connective tissue disorders. Although the exact mechanism of action is unknown, it may be based on ability of HCQ to bind to and alter DNA. HCQ has also been found to be taken up into the acidic food vacuoles of the parasite in the erythrocyte. This increases the pH of the acid vesicles, interfering with vesicle functions and possibly inhibiting phospholipid

metabolism. In suppressive treatment, HCQ inhibits the erythrocytic stage of development of plasmodia. In acute attacks of malaria, it interrupts erythrocytic schizogony of the parasite. Its ability to concentrate in parasitized erythrocytes may account for their selective toxicity against the erythrocytic stages of plasmodia infection. As an anti-rheumatic, HCQ is thought to act as a mild immunosuppressant, inhibiting the production of rheumatoid factor and acute phase reactants. It also accumulates in white blood cells, stabilizing lysosomal membranes and inhibiting the activity of many enzymes, including collagenase and the proteases that cause cartilage breakdown.

HCQ is also known to inhibit autophagy, a cellular process that may also lead to resistance to several cancer drugs, and as such, several trials have been conducted and shown safety of HCQ combined with several antineoplastic agents. However, no trials have tested HCQ in this setting and with the rationale and drug combination proposed in this trial. Additional detail is provided in the package insert in Appendix B.

#### **6.2.2 Source and dispensing of hydroxychloroquine**

Generic HCQ as 200 mg tablets will be obtained from a commercial source, Quality Prescription Drugs ([name]), a Canada-based company that uses U.S. sources that is both CIPA certified and Pharmacy Checker approved. The drug will be ordered for direct delivery to the Investigational Pharmacy at MD Anderson in batches to maintain at least a 3 months of supply on hand and will be dispensed as an investigational drug with standard logging of drug acquisition, dispensation and final accounting for disposition. Unused or returned drug will be destroyed. Drug will be dispensed to patients with the name and dosage drug, date dispensed, name of patients, name of study and instructions for use.

#### **6.2.3 Dosing of hydroxychloroquine and dose adjustments for hydroxychloroquine**

HCQ will be given by mouth at the assigned dose for the Phase I dose escalation and Phase II fixed dose parts of the trial. The dose of 400 mg daily was chosen as the starting dose for the Phase I portion as this is the usual dose used clinically and has been combined with endocrine and other and cancer therapies at this dose in prior studies.P34-37P There will be no dose adjustments for HCQ, and any grade 3 toxicity that is attributed to HCQ will require discontinuation of drug and for the patient to come off study. Subsequent treatment will be as per standard of care. For patients on the Phase I portion, any Grade III toxicity attributed to HCQ will also be counted as a dose-limiting toxicity if occurring in the first 28 days.

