### **3.8 Target Accrual**

A total of 54 patients will be enrolled to the study. This includes 2 to 18 patients (up to 6 per dose cohort at 400, 600 and 800 mg of HCQ daily and 6 at the RP2D, but as few as 2 patients in the unlikely event that the first 2 patients experience DLT at the lowest dose of HCQ (400 mg daily) and the study is halted.) in the Phase I metastatic portion, 6 patients for neo-adjuvant Phase II Part 1 and 30 patients for the Phase II Part 2 portion (25 needed for statistical plan and 5 expected to drop out). This does not account for replaced patients (as stated in Sections 3.6 and 3.7).

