### 5.2.3 Treatment Duration

#### 5.2.3.1 Phase I

Patients will receive treatment for at least until week 8 as long as there are no DLTs in the first 4 weeks, or significant toxicities requiring treatment discontinuation in the judgment of the treating investigator, and no evidence of clinical progression. At week 8, if tumor assessment by scans show evidence or response by RECIST 1.1 criteria (applies only to patients with

measurable disease), they will be allowed to stay on treatment as long as there is no evidence of progression or significant toxicities up to a maximum of 1 year. This maximum timeframe is due to concerns about HCQ toxicity, which could be duration-dependent. Patients who show progression or stability of disease at week 8 will come off study and can continue standard treatment (standard dose palbociclib and letrozole) or alternate therapy at the discretion of the treating physician.

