### **39. Warnings**

**PHYSICIANS SHOULD COMPLETELY FAMILIARIZE THEMSELVES WITH THE COMPLETE CONTENTS OF THIS LEAFLET BEFORE PRESCRIBING PLAQUENIL.**

Irreversible retinal damage has been observed in some patients who had received long- term or high-dosage 4-aminoquinoline therapy for discoid and systemic lupus erythematosus, or rheumatoid arthritis. Retinopathy has been reported to be dose-related.

When prolonged therapy with any Antimalarial compound is contemplated, initial (base line) and periodic (every three months) ophthalmologic examinations (including visual acuity, expert slit-lamp, funduscopic, and visual field tests) should be performed.

If there is any indication of abnormality in the visual acuity, visual field, or retinal macular areas (such as pigmentary changes, loss of foveal reflex), or any visual symptoms (such as light flashes and streaks) which are not fully explainable by difficulties of accommodation or corneal opacities, the drug should be discontinued immediately and the patient closely observed.

for possible progression. Retinal changes (and visual disturbances) may progress even after cessation of therapy.

All patients on long-term therapy with this preparation should be questioned and examined periodically, including the testing of knee and ankle reflexes, to detect any evidence of muscular weakness. If weakness occurs, discontinue the drug.

In the treatment of rheumatoid arthritis, if objective improvement (such as reduced joint swelling, increased mobility) does not occur within six months, the drug should be discontinued. Safe use of the drug in the treatment of juvenile arthritis has not been established.

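### The only explicit mandatory stop for HCQ is an attributed grade 3 toxicity; nothing clearly requires stopping for a lower-grade eye finding or muscle weakness, as the attached label advises

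*Combined protocol and SAP*

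**What the plan says.** Section 6.2.3 fixes the HCQ dose and names one mandatory stop: "any grade 3 toxicity that is attributed to HCQ will require discontinuation of drug and for the patient to come off study". It has no rule specific to the eye or to muscle.

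Section 5.2.3.1 governs Phase I treatment in two steps. Up to week 8, treatment may end for "significant toxicities requiring treatment discontinuation in the judgment of the treating investigator". After week 8, only RECIST responders continue, "as long as there is no evidence of progression or significant toxicities up to a maximum of 1 year". The reason for the cap follows: "This maximum timeframe is due to concerns about HCQ toxicity, which could be duration-dependent". Significant toxicity is not defined in either step. Section 3.8 plans "up to 6 per dose cohort at 400, 600 and 800 mg of HCQ daily".

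Section 6.2.1 points to the HCQ label: "Additional detail is provided in the package insert in Appendix B". In that label, the Warnings for lupus and rheumatoid arthritis open with "If there is any indication of abnormality in the visual acuity, visual field, or retinal macular areas", add visual symptoms that accommodation trouble or corneal opacities do not account for, and conclude that "the drug should be discontinued immediately and the patient closely observed". For long-term therapy they also call for periodic questioning and reflex testing, and for stopping the drug if weakness appears.

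In Table 1, eye examinations fall at baseline and off study only. Adverse event assessments continue on day 1 of each cycle after week 8. Section 5.2.6 allows later physical examinations to be limited to sites of disease.

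**The concern.** The protocol's stated threshold for stopping HCQ is higher than the one in its own appendix, for the toxicities that the label treats as reasons to stop without regard to severity. Appendix B says that early retinal dysfunction is usually reversible once the drug is stopped, but that retinal changes can progress even afterwards. It describes retinopathy as dose related and reported more often above the 200 to 400 mg/d maintenance range. The value of stopping early therefore lies below grade 3, where 6.2.3 is silent and 5.2.3.1 relies on an undefined term. Two investigators could handle the same early visual symptom differently, and both could be within the protocol.

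The protocol treats palbociclib differently: 6.1.4 has event-specific discontinuation rules for febrile neutropenia and for liver tests meeting Hy's Law. Exclusion criterion 2 bars entry for active visual disturbance at any grade, but no matching rule covers one that starts on HCQ.

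**Working it through.** **Stopping triggers side by side**

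| Source | Trigger | Grade threshold | Attribution needed |
|---|---|---|---|
| 6.2.3 | Toxicity attributed to HCQ | Grade 3 | Yes |
| 5.2.3.1, to week 8 | Significant toxicity requiring discontinuation | Undefined; investigator's judgment | Not stated |
| 5.2.3.1, after week 8 | Significant toxicity ends permission to continue | Undefined; no judgment qualifier | Not stated |
| Appendix B, eye | Any acuity, field or macular abnormality, or unexplained visual symptom | None | No |
| Appendix B, weakness (long-term therapy) | Weakness | None | No |

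No protocol row clearly captures the two label rows below grade 3.

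**Phase I patients exposed.** Section 8.0 gives 12 to 18 patients, which reproduces: 3 + 3 + 6 = 12 and 6 × 3 = 18. The documents give no week-8 response rate for this regimen, so 10% to 40% is assumed.
- Low end: 12 × 0.10 = 1.2 responders.
- High end: 18 × 0.40 = 7.2 responders.
- Probability of at least one responder at the low end: 1 − 0.90^12 = 0.72.
- Outer check with the palbociclib label's 55.3% response rate (125 mg, measurable disease): 12 × 0.553 = 6.6 to 18 × 0.553 = 10.0.

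**Duration after week 8.** 52 − 8 = 44 weeks. One year is 52/4 = 13 cycles, so day 1 of cycles 3 to 13 gives 11 scheduled adverse event assessments.

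**Dose.** 600/400 = 1.5 and 800/400 = 2.0 times the top of the maintenance range. At most 6 + 6 = 12 of 18 patients would be at 600 or 800 mg/d.

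**Phase II.** Sections 1.3, 1.4 and 5.2.2 describe patients staying on therapy or on study to weeks 16 to 24. If HCQ continued, exposure would be 16 − 2 = 14 to 24 − 2 = 22 weeks. Section 5.2.3.2 instead moves patients to surgery or standard of care after T2, which leaves about 14 days of HCQ.

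**Stops for unrelated symptoms under a stricter rule.** Appendix A reports blurred vision in 3.6% and asthenia in 17% on palbociclib plus letrozole, over a median 19.8 months at 125 mg/d.
- Blurred vision among responders: 1.2 × 0.036 = 0.04 to 7.2 × 0.036 = 0.26.
- Blurred vision if all 18 Phase I patients continued: 18 × 0.036 = 0.65.
- Blurred vision across all 54 planned patients, since the eye rule would apply at any time: 54 × 0.036 = 1.9. This is a generous figure, because most would have far shorter exposure than 19.8 months.
- Asthenia if all 18 continued: 18 × 0.17 = 3.1. This is why weakness should be confirmed on examination.

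**Harm.** Appendix B gives no event rate and calls onset within several months rare. The expected number of retinal or muscle events cannot be derived.

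**The case against.** The best defence is that 6.2.3 sets a floor. It does not say that HCQ continues below grade 3, and after week 8 section 5.2.3.1 makes the absence of significant toxicity a condition of staying on treatment. That stands. A reader might infer that the protocol directs dosing through lower-grade eye symptoms, or leaves the decision for responders wholly to the investigator. The text supports neither: the judgment qualifier belongs to the period up to week 8. What remains is that the condition has no content for eye or muscle findings.

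A second defence is that the risk is already managed. Retinal disease and active visual disturbance are excluded, a normal baseline retinal examination is required, the examination is repeated off study, and treatment is capped at 1 year. Section 7.4 covers events found by questioning or examination, and Appendix B tells prescribers to know its contents. These measures reduce risk, but none is a stop for onset during treatment, and 6.2.1 cites Appendix B only for further detail.

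Third, the benchmark can be disputed. Appendix B does not define long-term therapy, so applying its weakness rule from week 8 is a reviewer's choice. It also permits 400 mg once or twice daily initially in lupus and 400 to 600 mg/d initially in rheumatoid arthritis. The dose comparison therefore shows exposure above maintenance level, not a breach of the label.

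Finally, no endpoint or analysis is affected and no harm can be counted. That is fair, and it sets the severity.

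**Conclusion.** The point holds as a minor safety clarification. The one explicit mandatory HCQ stop is looser than the attached label, and the condition that could close the gap is undefined. Those chiefly affected are about 1 to 7 Phase I responders, with up to 44 further weeks on HCQ. This rests on the assumed 10% to 40% response rate; the ceiling is 18. Any Phase II patient kept on HCQ beyond T2 would be added, and the documents conflict on whether there are any.

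Two stronger readings should be resisted. One is that early retinal or muscle findings would necessarily be graded below 3: the CTCAE tables are not in the documents, so no grade can be assigned. The other is that a material number of patients would be harmed: no rate is given, and the number is likely small. The case for acting is that the harm may be irreversible and the rule is cheap.

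**What to change.** Add to 6.2.3 that, regardless of grade, HCQ is stopped:
- at any time on HCQ, for a new visual-acuity, visual-field or macular abnormality, or for visual symptoms not explained by accommodation or corneal opacities;
- for patients on HCQ beyond week 8, for muscle weakness confirmed on examination, not fatigue or asthenia alone.

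State in 5.2.3.1 that these count as significant toxicities. Ask about vision and weakness at the adverse event assessments already in Table 1, and let a positive weakness answer prompt a strength and reflex check despite the limited examination that 5.2.6 allows. Leave the DLT definition in 3.3 unchanged. The eye rule should not be confined to the period after week 8 to protect evaluability, because that would write the departure from the label into the protocol.

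The cost is a few lines of text and two questions at existing visits. An occasional patient will stop HCQ for an unrelated symptom, and a Phase I responder would then lose a regimen that was working. A patient who stops within the DLT or Ki67 window may need replacement under 3.7. Symptom questions will not find asymptomatic retinal change. Appendix B advises eye examinations every three months in prolonged therapy; whether to add them is a separate decision for the sponsor.
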